5.5 Study size

This study will have an approximate enrollment of 300 patients diagnosed with MF-CTCL who are being treated with Valchlor (newly initiated or continuing treatment).

A sample size of 270 evaluable patients is needed to estimate the percentage of patients with clinical status and the percentage of patients with hospitalizations, both with a margin of error of 6 percentage points. Assuming that up to 10% of patients may be non-evaluable due to incomplete follow-up, the sample size target for enrollment should be 300.

It is projected that approximately 200 evaluable patients will be re-consented under Amendment 1. The margin of error for 200 evaluable patients will be 7%.

Additionally, it is important to be able to estimate these same percentages with a margin of error of 10 percentage points or less for key subgroups representing a third or more of the patient population (e.g., patients newly initiating Valchlor). A total of 100 patients are required to achieve a margin of error of 10 percentage points per subgroup, so that a total enrollment of 300 patients is needed.

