## ANALYSIS POPULATIONS

This study will enroll approximately 300 MF-CTCL patients who are being treated (newly initiated or continuing treatment) with Valchlor from up to 50 participating university-affiliated hospitals, community hospitals, or community clinics in the United States.

Patients considered 'being treated with Valchlor' are composed of two distinct groups:

- 1) Patients who are newly initiating Valchlor treatment (i.e. patients who have initiated Valchlor within 30 days or fewer prior to enrollment) and,
- 2) Patients who are continuing treatment with Valchlor (i.e. patients who have been on Valchlor for more than 30 days prior to enrollment).

Patients in either group must be treated with Valchlor at enrollment to be eligible for the study.

All consecutive MF-CTCL patients who are receiving Valchlor at participating US centers are eligible for enrollment in the study, regardless of other MF-CTCL therapies received before or at the time of enrollment.

The primary efficacy endpoint will be the proportion of subjects who are responders to treatment at the 12-month timepoint using a  $\geq 50\%$  reduction from baseline in BSA as the definition of a responder in the group of patients who used mechlorethamine plus corticosteroids and possibly another treatment. Since PROVe did not require a specific visit schedule, the primary 12-month analysis will include patients with a post-baseline % BSA score that falls within a window of  $365 \pm 90$  days. Please note that in this observational trial, patients continued on study even if they permanently discontinued mechlorethamine gel for any reason and switched to new therapy. Given this, such patients (15-20%) will be excluded from the analysis at 12 months. A sensitivity analysis will be conducted for the primary analysis using the full dataset. We will compare this to the subset of patients who discontinued mechlorethamine gel (Table 21a).

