A minimum sample size threshold of N=20 subjects will be required to conduct a statistical analysis. This minimum is set to ensure that the effect size measurements for the various endpoints (typically using a within treatment change from baseline approach) are reasonable estimates of the true population values. Prior prospective publications that evaluated mechlorethamine clinical response have had similar sample sizes (Liner K. [Drug Des Devel Ther.](#) 2018 Jan 31;12:241-254). With this analysis filter in place the total number of analyses will be determined after the available sample size for each analysis is established. Summary statistics will be provided for endpoints with sample sizes that range from 10 to 19 patients, and no endpoint values will be provided for endpoints with sample sizes with less than 10 patients with the exception of sub-groups for the by-time analysis.

The primary data set from the pre-analysis sample size assessment was selected as patients who used mechlorethamine plus corticosteroids plus possibly another treatment. For all potential endpoints, there were not adequate numbers of mechlorethamine monotherapy treaters that exceeded the N=20 minimum sample size. The following analysis populations will be applied to the primary and secondary endpoints in the study:

1. Valchlor + corticosteroids + possibly another treatment (primary) (V+C+other)
2. Valchlor + phototherapy + possibly another treatment (V+P+other)
3. Valchlor + oral bexarotene + possibly another treatment (V+B+other)
4. Valchlor + any other treatment (V+other)

These groups were selected prior to conducting any analysis on the basis that there were at least 30 patients who received the concomitant MF-CTCL therapy in combination with Valchlor.

Based on discussions with the principle investigator the section II. and III. analyses will be excluded. The difference between continuing and new mechlorethamine users is on average only 3 months, so the new versus continuing comparisons are not clinically much different.

II. Continuing Mechlorethamine Patients

1. Valchlor + corticosteroids + possibly another treatment (primary)
2. Valchlor + phototherapy + possibly another treatment
3. Valchlor + oral bexarotene + possibly another treatment
4. Valchlor + any other treatment

III. New Mechlorethamine Patients

1. Valchlor + corticosteroids + possibly another treatment (primary)
2. Valchlor + phototherapy + possibly another treatment

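### The SAP says a minimum of N=20 ensures reasonable estimates, but N=20 gives up to ±22 points for a response rate, and no response rate has a planned confidence interval

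*SAP*

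**What the plan says.** Protocol 5.5 bases the sample size on precision; it gives no hypothesis or power calculation. It needs 270 evaluable patients to estimate the percentages for clinical status and hospitalization, "both with a margin of error of 6 percentage points". For the extended follow-up, "The margin of error for 200 evaluable patients will be 7" per cent. For key subgroups that make up a third or more of the population, "A total of 100 patients are required to achieve a margin of error of 10 percentage points per subgroup".

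The SAP, under Analysis Populations, makes the main result a percentage: "The primary efficacy endpoint will be the proportion of subjects who are responders to treatment at the 12-month timepoint", with response defined as a BSA reduction of at least 50%. The by-time BSA analyses, ORR2 and ORR4 are also responder percentages.

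The same section sets the size rule: "A minimum sample size threshold of N=20 subjects will be required to conduct a statistical analysis". The reason follows: "This minimum is set to ensure that the effect size measurements for the various endpoints", in most cases within-treatment changes from baseline, "are reasonable estimates of the true population values". The SAP adds that earlier prospective publications had similar sample sizes. It gives no interval width. Endpoints with 10 to 19 patients get summary statistics. No values are shown for endpoints "with less than 10 patients with the exception of sub-groups for the by-time analysis".

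The SAP's Statistical Methods section names no confidence interval. In Appendix A, the shells for Tables 21-24 carry only row labels, three staging columns and N. Table 25 (time to next treatment) is the only shell with a 95% CI.

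**The concern.** In a study sized only on precision, the width of the interval is the main thing a reader needs beside each percentage. The SAP instead gives a general assurance that N=20 is enough and plans no interval for its primary endpoint. Small cells are likely. Table 22 alone has 9 time points × 6 rows × 3 staging columns = 162 cells, and the by-time exemption lets cells below N=10 be printed. A reader could take chance variation between rows for a real difference, or apply the protocol's margins to groups that are much smaller than those it was sized for.

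**Working it through.** **Inputs.** Protocol 5.5: margins of 6, 7 and 10 points at n = 270, 200 and 100. SAP Analysis Populations: thresholds of 20 and 10, and a 15-20% exclusion from the 12-month analysis. SAP Table 28 shell: 88 (30%) of 289 patients on topical corticosteroids during mechlorethamine treatment. The confidence level and p are not stated; 95% and p = 0.5 are assumed.

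**Step 1: reproduce the plan's own figures.** Half-width = 1.96 × √(p(1−p)/n), with p = 0.5.

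| n | Computed | Protocol |
|---|---|---|
| 270 | 5.96 points | 6 |
| 200 | 6.93 points | 7 |
| 100 | 9.80 points | 10 |

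All three reproduce. A 90% level would give 5.0, 5.8 and 8.2, and a 99% level 7.8, 9.1 and 12.9, so 95% at p = 0.5 is the basis that fits. Enrollment also reproduces: 270 / 0.90 = 300.

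**Step 2: same formula at the SAP's thresholds.**

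- N = 20: 1.96 × √(0.25/20) = 21.9 points. Exact (Clopper-Pearson) interval for 10 of 20: 27.2% to 72.8%. Wilson: 29.9% to 70.1%. At a true rate of 20% the half-width is 17.5 points.
- N = 10: 1.96 × √(0.25/10) = 31.0 points. Exact interval for 5 of 10: 18.7% to 81.3%.
- N = 5, possible under the by-time exemption: 3 responders of 5 has an exact interval of 14.7% to 94.7%.

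**Step 3: mean changes.** The SAP's parenthesis points to change from baseline. The 95% half-width for a mean at N = 20 is t(0.975, 19)/√20 = 2.093/4.472 = 0.47 SD. The SAP does not state this either.

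**Step 4: indicative margin for the primary.** The documents give no N for the primary group. If the 88 topical corticosteroid users in the Table 28 shell approximate it (an inference), then at p = 0.5:

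- N = 88: 1.96 × √(0.25/88) = 10.4 points, before the stage IA/IB restriction, the requirement for a BSA value within 365 ± 90 days, and the 15-20% exclusion.
- If the exclusion applies evenly to the 88 (an assumption), 88 × 0.80 = 70.4 and 88 × 0.85 = 74.8 remain, giving 11.7 and 11.3 points. The stage and window filters can only reduce N further; the documents do not say by how much.

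These are worst cases over p. At N = 88 the half-width is 8.4 points for a true rate of 20% or 80%, and it is 10 points or less when the true rate is below about 36% or above about 64%.

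**The case against.** The strongest reply is that the SAP breaks no rule. The protocol's margins were set for clinical status and hospitalization, not BSA response, and its 10-point target covers subgroups of a third or more. In the Table 28 shell, corticosteroid users are 88/289 = 30.4%, phototherapy users 11% and systemic retinoid users 12.5%, all below a third. This stands. A reader might infer that any result with fewer than 100 patients fails a protocol standard; the protocol sets no such standard for these groups.

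A reader might also take 10.4 points as the best margin the primary can reach. It is the p = 0.5 worst case at N = 88, and other true rates give narrower intervals. Nor do the documents make 88 a fixed ceiling: the row is a pre-filled shell line for topical corticosteroids, while the population name says only corticosteroids. Topical is the only corticosteroid line in the therapy tables, which makes the inference reasonable but no more than that.

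The SAP sentence mainly has change from baseline in mind, so ±22 points should not be applied to every endpoint. That is fair, but the sentence covers the various endpoints, and the primary, by-time BSA, ORR2 and ORR4 are percentages. The similarity to earlier publications supports the choice of N by precedent; it does not state a precision.

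It might be inferred that the SAP commits to counts and percentages only for its endpoints. That line in Statistical Methods concerns enrollment characteristics. The missing interval is an omission, not a declared choice.

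Finally, protocol 5.7.4 calls the response summary descriptive and not an estimate of efficacy, and the SAP treats its p-values as descriptive. That limits the harm. It does not remove the need for an interval around a percentage that the SAP itself names as the primary efficacy endpoint.

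**Conclusion.** The point holds as a gap in stated precision and reporting. The SAP's assurance about N=20 is unsupported for the responder endpoints: on the basis that reproduces the protocol's own margins, N=20 allows up to ±21.9 points, more than twice the 10 points the protocol sought for key subgroups. No interval is planned for any response rate, and the by-time exemption waives the SAP's safeguard where cells are likely to be smallest. The figures assume 95% confidence and p = 0.5. The figures for the primary also rest on the inferred 88 and the even exclusion.

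The documents contain no arithmetic error on this point, and it biases no estimate and affects no decision rule. It is a cheap improvement that would change what a reader can conclude from the tables; it need not hold up the plan.

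**What to change.** 1. Report an exact or Wilson 95% confidence interval with every response percentage in Tables 21-24, and a t-based 95% interval with every mean change in Tables 27a-c.
2. Replace the assurance about N=20 with actual half-widths at N=20 and N=10 (21.9 and 31.0 points for a percentage), stating the confidence level and p; for mean changes, give the corresponding width in SD units (0.47 SD at N=20).
3. Remove the by-time exception to the rule on fewer than 10 patients.
4. State the expected margin for the primary at its actual N, after the stage, BSA-window and discontinuation criteria, labelled as the worst case at p = 0.5.

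Cost: a column in the shells, a few sentences in the SAP, and a stated precision that looks less favourable. More of the small by-time cells would be blank. No new data or change of design is needed.

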The by-time analyses for each visit will provide supportive clinical and statistical mechlorethamine response data over the whole treatment period, before and after the 12 month results. Patient visits were variable throughout the study and no defined patient visits were required in PROVe. Given this construct, the By-Visit analyses of % BSA data, Pruritis VAS, Skin-Dex 29, and the MF/SS CTCL QOL instrument will be constructed from the respective change from baseline that occurred closest to each of the following timepoints 1, 3, 6, 9, 12, 15, 18, 21 and 24 months, and will include data that falls within  $\pm 45$  days of each designated timepoint.

Other secondary endpoints include:

- Overall Response Rate 2 (ORR2) Percent of patients with  $\geq 50\%$  reduction from baseline in % Body Surface Area of disease for at least two consecutive visits.
- Overall Response Rate 4 (ORR4) Percent of patients with  $\geq 50\%$  reduction from baseline in % Body Surface Area of disease for at least four consecutive visits.
- Time to Next Treatment (TTNT). TTNT is defined as the median number of days an individual patient stayed on a treatment before starting a new treatment or adding on an additional treatment.
- Rates of on Study Hospitalization
- Pruritis VAS
- SkinDex-29

- MF/SS CTCL – QOL Instrument

For each endpoint, separate analyses will be done for patients contributing data with IA and IB staging, all staged patients, and all patients regardless of staging. As PROVe is an observational study, an Intent-to-Treat (ITT) population analysis is not applicable. There are no cases where an intention to treat was prevented and therefore no potential for a selection bias in the analyses prespecified in this SAP. This results in a total of 51 analysis types as shown in the Figure 1 below.

Figure 1: Analysis Populations for the PROVe Study

	Patients Contributing Data			Totals:
	IA and IB Staging	All Staged	All Patients with and without Staging	
Primary Endpoint	1	1	1	3
9 By-Time Analyses	9	9	9	27
7 Other Secondary Endpoints	7	7	7	21
			Overall Total:	51

These analyses will be applied to following four (4) analysis populations:

1. Valchlor + corticosteroids + possibly another treatment (primary) (V+C+other)
2. Valchlor + phototherapy + possibly another treatment (V+P+other)
3. Valchlor + oral bexarotene + possibly another treatment (V+B+other)
4. Valchlor + any other treatment (V+other)

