## ASSESSMENT SCHEDULE

Demographics, medical history, current and historical MF-CTCL treatments, clinical status by physician, clinical status assessments, the Visual Analogue Scale (VAS) for pruritus, the Skindex-29, and ongoing adverse events (AEs) and serious adverse events (SAEs) related to Valchlor are collected at the enrollment visit, per routine clinic visits. Any data that is not collected at enrollment or present in the historical patient information will be indicated as not assessed, not applicable or not done, as appropriate. In addition, to appropriately construct change from baseline analyses all baseline data must be verified as such. For example, if a % BSA score is provided at enrollment, it may not represent a baseline disease score if a subject was already using mechlorethamine prior to the collection of that score. The same handling should apply to the PRO questionnaires.

Change in TNMB classification, change in medical history, change in medications with Valchlor and other MF-CTCL treatments, HCU, clinical status by physician, clinical status assessments, VAS for pruritus, the Skindex-29, reports of secondary exposure, and all AEs and SAEs related and unrelated during Valchlor use and >30 days after Valchlor discontinued are collected at follow-up visits during the observation period, as recorded during the routine clinic visit. These visits occur at the physician's discretion (i.e., they are not scheduled per protocol); consequently, the number of follow-up visits will vary across patients. Additionally, the data collected during the visits will be dependent upon routine clinic practice, and thus not all data may be available.

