### **Other MF-CTCL Treatments**

Other MF-CTCL medications will be categorized by specific therapies (skin-directed therapies, systemic therapies and other) and identified by comparing the start/stop dates of the various medications/therapies recorded on the Other MF-CTCL Treatments Log with the date of enrollment from the Enrollment eCRF. A table summarizing pre-treatments and therapies that were stopped prior to enrollment will be included, as well.

Patients will be considered to be on other medications/therapies (specific for MF-CTCL). The data will include the medication/therapy start date either on the day of enrollment or before the day of enrollment and have either continued or stopped taking the medication after the day of enrollment. By this algorithm, patients who start a medication on the day of enrollment will be considered to be on that medication at enrollment, patients who start and stop a medication on the day of enrollment will be considered to be on that medication at enrollment, but patients who stop a medication on the day of enrollment will not.

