### **Healthcare Resource Utilization**

Hospitalizations and ER visits that occur during the course of the study will be reported in a table summarizing the rate of hospitalizations and the rate of ER visits will be presented. Data will come from the Healthcare Resource Utilization module on the eCRF. The denominator will be based on the sum of follow-up time available for all subjects. Only hospitalizations and ER visits that occur post-enrollment will be included in the numerator. These will be reported separated as continuing Valchlor versus newly initiated Valchlor patients.

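### No SAP table gives adverse-event or dermatitis incidence, or time to next treatment, for the full Valchlor cohort, because every analysis population requires a co-therapy

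*SAP*

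**What the plan says.** SAP, Analysis Populations, names four groups: Valchlor with corticosteroids, with phototherapy, with oral bexarotene, and with any other treatment. The groups were chosen on concomitant therapy, with at least 30 patients on it, so none of them admits a patient using Valchlor alone. On monotherapy the section says, for all potential endpoints, that "there were not adequate numbers of mechlorethamine monotherapy treaters that exceeded the N=20 minimum sample size". It prints no count and does not define the term. The N=20 minimum and the four populations are tied to the primary and secondary endpoints, and adverse events (AEs) are not among these. The same section drops the breakdown by continuing and new users: "the section II. and III. analyses will be excluded".

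The shells follow the four groups. Tables 16, 18 and 19 have one column per group. Tables 25 and 26 have one row per group, plus two corticosteroid-phototherapy combinations. In Tables 25 and 26 the column for patients with and without staging widens stage only. The Overall line in Tables 18 and 19 means any recorded event, not all patients.

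Other parts of the plan are wider:
- Estimating dermatitis incidence among Valchlor users is an objective (protocol Section 4; SAP, Analysis Objectives).
- Protocol Section 5.7.5 plans AE summaries with no co-therapy limit and separate detail for dermatitis. The SAP's list of tables has no dermatitis table.
- On hospitalization rates, SAP, Healthcare Resource Utilization, says "The denominator will be based on the sum of follow-up time available for all subjects" and asks for continuing and newly initiated patients to be reported separately.
- Time to next treatment (TTNT) is time on a treatment "before starting a new treatment or adding on an additional treatment".

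**The concern.** As the shells stand, AE incidence would be tabulated only for co-treated patients. A reader could not rebuild the full-cohort figure. The groups overlap, since a patient on corticosteroids and phototherapy belongs to at least two of them, so their counts cannot be summed. Patients on Valchlor alone appear in none of them. A stated safety objective would then have no planned estimate in the population it names. AEs in co-treated patients may also differ from those in patients on Valchlor alone, and the tables could not show whether they do.

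The reason given for having no Valchlor-alone group is a small count. It is offered across endpoints that need very different data, and the SAP's own treatment table appears hard to square with it for some of them.

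**Working it through.** **Inputs, all from SAP Table 28 (N=289)**

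| Class | Before mechlorethamine | During mechlorethamine |
|---|---|---|
| Skin-directed therapy | 226 (78%) | 125 (43%) |
| Systemic therapy | 83 (29%) | 47 (16%) |

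**1. Do the printed figures hold together?** 125/289 = 43.25%, 47/289 = 16.26%, 226/289 = 78.2% and 83/289 = 28.7%, all as printed after rounding. The filled rows during treatment sum to 33+16+1+88+9+7 = 154 for skin-directed and 11+36+6 = 53 for systemic therapy. Both exceed the class totals, as expected if the totals count each patient once. I take 125 and 47 as complete patient counts. The table is a partly filled shell, so this is an assumption.

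**2. Patients with no listed co-therapy during Valchlor.** The number with at least one listed co-therapy lies between max(125, 47) = 125 (full overlap) and 125 + 47 = 172 (no overlap).
- 289 − 172 = 117 (40.5%)
- 289 − 125 = 164 (56.7%)

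**3. What moves this range.** The SAP has a third class of MF-CTCL therapy, simply called other, and Table 28 has no row for it. Patients whose only co-therapy is in that class would lower the count. In the other direction, the SAP says other therapies are "identified by comparing the start/stop dates of the various medications/therapies recorded on the Other MF-CTCL Treatments Log with the date of enrollment", but it does not tie that rule to the four populations. If it applied, patients who start a co-therapy after enrollment would also belong to no group, and the number left out would rise.

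**4. The N=20 statement.** If monotherapy means no other therapy during Valchlor, a count of 20 or fewer needs at least 269 co-treated patients.
- No overlap: 269 − 172 = 97 patients (33.6% of 289) on other therapy only.
- Full overlap: 269 − 125 = 144 patients (49.8%) on other therapy only.

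If monotherapy also excludes prior therapy, at most 289 − 226 = 63 patients qualify. The lower limit is 0, because 226 + 83 = 309 exceeds 289. The statement could then be true.

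**5. Which endpoints could the statement cover?** Body surface area and questionnaire endpoints need a value in the time window and a true baseline, since "all baseline data must be verified as such". The usable count there may well be 20 or fewer. Hospitalization rate needs only event counts and follow-up time, and TTNT needs only treatment dates, which the eCRF collects. For AEs the filter does not apply at all.

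**6. Full-cohort precision.** Protocol Section 5.5 seeks a 6-point margin for the percentage hospitalized: 1.96 × √(0.25/270) = 5.96 points. With all 289 patients it is 1.96 × √(0.25/289) = 5.8 points, so a full-cohort estimate meets the protocol's own target.

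**7. Hospitalization text against shells.** Healthcare Resource Utilization wants continuing and new patients reported separately. Analysis Populations excludes the continuing and new analyses. Tables 16 and 26 show only co-therapy groups. One set of tables cannot satisfy all three.

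**8. TTNT group membership.** The event is starting or adding a therapy. With no date fixed for membership, the same act could place a patient in a group and end that patient's TTNT, while a patient who never adds a therapy appears in no row. The SAP also gives no TTNT time origin. The documents do not allow the size of this effect to be worked out.

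**The case against.** Several counter-arguments have force.

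- *The count is soft.* This stands. A reader might take 117 to 164 as firm limits on the number of patients left out. They are not, for the reasons in step 3.
- *The N=20 statement may be true.* A reader might infer that Table 28 refutes it. The documents do not go that far. It may hold for body surface area and questionnaire endpoints, under a definition that excludes prior therapy, or within a staging column: exceeding 20 in stage IA/IB needs an IA/IB share of 21/164 = 12.8% to 21/117 = 17.9% of the monotherapy patients, and no share is given. It can also be read as saying only that the numbers were not adequate for every endpoint. Even so, it would give no reason to omit the endpoints that have enough patients.
- *The SAP text does not restrict AEs.* The AE paragraph in Statistical Methods names no co-therapy group, and protocol Section 5.7.5 is not withdrawn. So this is a mismatch between text and shells rather than a stated rule. But that section's default is the analysis population, and the shells leave no place for a total.
- *The events are not lost.* Listings 1 to 3 and 9 are not confined to the four groups, so it would be wrong to infer that safety data are withheld. Listings give no incidence, however. The comparison of contributing and non-contributing patients under Methods for Handling Missing Data is required only for results meant for dissemination, and it does not supply the missing estimate.
- *The hospitalization denominator can be read as pooled follow-up within each reported group.* That is fair, and it removes the conflict over the denominator. The conflict over the continuing/new split remains.

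**Conclusion.** The point holds for coverage. No SAP table gives AE incidence, dermatitis incidence or TTNT for all Valchlor patients, and for AEs and dermatitis this leaves a stated objective without its estimate. It should be fixed before the tables are programmed.

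Roughly 117 to 164 of 289 patients (40.5% to 56.7%) had no listed skin-directed or systemic therapy during Valchlor. This assumes that the Table 28 class totals are complete, and it is approximate in both directions. The gap in the shells does not depend on the exact number.

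The N=20 statement cannot be checked as written. Only if monotherapy means no other therapy during Valchlor does Table 28 fail to support it for hospitalization and TTNT. The hospitalization and TTNT items are matters of reconciliation and definition, and no bias of a given size is claimed for either.

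**What to change.** 1. Add an All Valchlor patients column or row to Tables 16, 18, 19, 25 and 26.
2. Add a dermatitis incidence summary in all Valchlor patients, as protocol Section 5.7.5 foresees.
3. Define monotherapy, saying whether prior therapy counts, and replace the N=20 sentence with the monotherapy count for each endpoint. Show a Valchlor-alone group for hospitalization and TTNT where its N is at least 20. An other-therapy-only row in Table 28 would make the count checkable.
4. Reconcile the continuing/new split in Healthcare Resource Utilization with Analysis Populations and with the Table 16 and 26 shells.
5. For TTNT, state the time origin and fix group membership by the therapies in use at that origin. Enrollment is not a safe default: continuing patients started Valchlor more than 30 days before it, so if the clock starts at initiation, an enrollment-date rule would set membership after the clock had begun.

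The cost is a few shell rows or columns, one added summary and SAP wording. No new data are needed.
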